2.1.3 Phase II Inclusion Criteria

- Phase II patients must meet the following Eligibility Criteria in addition to the General Criteria described above. Patients may have had treatment for no more than 1 prior relapse (i.e. failed 2 lines of treatment-initial therapy and therapy for first relapse) at 2nd relapse, treatment per BTTC09-01 is an option; see relapse and treatment count

table below). Relapse is defined as progression following initial therapy (i.e. radiation+/- chemo if that was used as initial therapy). The intent therefore is that patients had no more than 2 prior therapies (initial and treatment for 1 relapse). If the patient had a surgical resection for relapsed disease and no anti-cancer therapy was instituted for up to 12 weeks, and the patient undergoes another surgical resection, this is considered as 1 relapse. For patients who had prior therapy for a low-grade glioma, the surgical diagnosis of a high-grade glioma will be considered the first relapse.

Relapse and Treatment Count		
Initial diagnosis →	Surgical resection	Radiation + Chemotherapy #1
Relapse #1 →	+/- Surgical resection	Chemotherapy #2
Relapse (#2) →	Patient to be evaluated for enrollment to BTTC09-01	

- Patients must not have received prior therapy with sorafenib, everolimus, or related drugs such as tyrosine kinase inhibitors, VEGF inhibitors (except bevacizumab), or mTOR inhibitors.

2.1.4 General Exclusion Criteria

- 2.1.4.1 Patients has any significant medical illnesses that in the investigator’s opinion cannot be adequately controlled with appropriate therapy or would compromise the patient’s ability to tolerate this therapy
- 2.1.4.2 Patients with a history of any other cancer (except non-melanoma skin cancer or carcinoma in-situ of the cervix), unless in complete remission and off of all therapy for that disease for a minimum of 3 years are ineligible.
- 2.1.4.3 Patient has an active infection or serious intercurrent medical illness.
- 2.1.4.4 Patient has any disease that will obscure toxicity or dangerously alter drug metabolism.
- 2.1.4.5 Patients is on an enzyme inducing anti-convulsants. If patients were previously on EIAEDs and these have been discontinued, patients must have been off the agent for at least 2 weeks prior to first study drug administration. For patients who need to start an AED or the AED needs to be changed, it is strongly recommended that all efforts should be made to use a non-EIAED.
- 2.1.4.6 Patients who have any severe and/or uncontrolled medical conditions or other conditions that could affect their participation in the study such as: Symptomatic congestive heart failure of New York heart Association Class III or IV unstable angina pectoris, symptomatic congestive heart failure, myocardial infarction within 6 months of start of study drug or any other clinically significant cardiac disease severely impaired lung function as defined as spirometry and DLCO that is 50% of the normal predicted value and/or O2 saturation that is 88% or less at rest on room air, uncontrolled diabetes as defined by fasting serum glucose >1.5 x ULN, active (acute or chronic) or

- uncontrolled severe infections, liver disease such as cirrhosis, chronic active hepatitis or chronic persistent hepatitis.
- 2.1.4.7 Cardiac ventricular arrhythmias requiring anti-arrhythmic therapy.
 - 2.1.4.8 Uncontrolled hypertension defined as systolic blood pressure > 140 mmHg or diastolic pressure > 90 mmHg, despite optimal medical management.
 - 2.1.4.9 Known human immunodeficiency virus (HIV) infection or chronic or acute Hepatitis B or C. Note: Patients who have a history of HBV and HCB infection are eligible, however, they must receive prophylactic antiviral therapy for 1-2 weeks prior to receiving study drug (see Section **3.3.2**)
 - 2.1.4.10 Thrombotic or embolic events (except DVT or pulmonary embolus) such as a Cerebrovascular accident including transient ischemic attacks within the past 6 months.
 - 2.1.4.11 Pulmonary hemorrhage/bleeding event \geq CTCAE Grade 2 within 4 weeks of first dose of study drug.
 - 2.1.4.12 Any other hemorrhage/bleeding event \geq CTCAE Grade 3 within 4 weeks of first dose of study drug.
 - 2.1.4.13 Serious non-healing wound, non-healing ulcer, or bone fracture.
 - 2.1.4.14 Evidence or history of bleeding diathesis or coagulopathy
 - 2.1.4.15 Major surgery, open biopsy or significant traumatic injury within 4 weeks of first study drug.
 - 2.1.4.16 Use of St. John's Wort, orrifampin (rifampicin), or other strong CYP34A inducers. Dexamethasone is okay as long as the dose is 16 mg /day or less. Note: Patients who are on the above referenced medications may be considered eligible with a washout period of 14 days. Contact the coordinating center to discuss patients with the above aforementioned agents before patient registration.
 - 2.1.4.17 Known or suspected allergy to sorafenib, everolimus, or any agent given in the course of this trial.
 - 2.1.4.18 Any condition that impairs patient's ability to swallow whole pills.
 - 2.1.4.19 Any malabsorption problem.
 - 2.1.4.20 Other malignancies within the past 3 years except for adequately treated carcinoma of the cervix or basal or squamous cell carcinomas of the skin.
 - 2.1.4.21 Female patients who are pregnant or breast feeding, or adults of reproductive potential who are not using effective birth control methods. Barrier contraceptives must be used throughout the trial by both sexes. Hormonal contraceptives are not acceptable as a sole method of contraception. (Women of childbearing potential must have a negative urine or serum pregnancy test within 7 days prior to administration of everolimus and sorafenib).
 - 2.1.4.22 Patients who have received prior treatment with an mTOR inhibitor (sirolimus, temsirolimus, everolimus).

- 2.1.4.23 Patients with a known hypersensitivity to everolimus or other rapamycins (sirolimus, temsirolimus) or to its excipients.
- 2.1.4.24 History of noncompliance to medical regimens.
- 2.1.4.25 Patients unwilling to or unable to comply with the protocol.
- 2.1.4.26 Patients on total daily dose of dexamethasone greater than 16 mg.

2.2 SCREENING EVALUATION

Prior to registration on the study, all patients will undergo the following screening tests within 14 days of registration:

- A complete medical history, concomitant medication review, physical exam with vital signs (heart rate, blood pressure, respiration rate, height and weight) and neurological examination (to include documentation of the patients Karnofsky Performance Status per Appendix [13.1](#))
- Neuro-imaging confirming tumor progression shall be performed on all patients. The scan done prior to study entry documenting progression will be reviewed by the patient's treating physician to confirm progression of disease.
- Pre-study tests shall include ECG chest X-ray (or CT scan with lung windows) within 30 days of treatment, and laboratory studies including CBC, differential, platelets, serum creatinine, phosphate, lipase, amylase, bilirubin, SGOT, PT, PTT, fasting serum glucose and lipid panel, urinalysis with microanalysis, HBV-DNA, HbsAg, HBsAb (Qualitative), HBcAb, HCV-RNA-PCR and serum pregnancy test for women of childbearing potential. All patients should be screened for hepatitis risk factors and any past illnesses of hepatitis B and hepatitis C infection. All patients with positive HBV-DNA or HBsAg should be treated prophylactically with an antiviral (i.e. Lamivudine) for 1-2 weeks prior to receiving study drug (see Section [3.3.2](#)). The antiviral treatment should continue throughout the entire study period and for at least 4 weeks after the last dose of everolimus. Patients with viral hepatitis C risk factors should be screened for HCV RNA-PCR. UPC ratio must be obtained if urinalysis has >2+ protein. Pre-study tests (except pregnancy test) must be obtained within 14 days of registration. Pregnancy test must be obtained within 7 days prior to starting the study drugs.
- Documentation of tumor diagnosis. Following registration, slides from the most recent pre-registration biopsy or resection must be submitted for review to local institution if surgery was not done there.
- Neuro-imaging confirming tumor. (See section [2.5](#))

2.3 REGISTRATION PROCEDURES

Patients who are candidates for the study will first be evaluated for eligibility by the local investigator. All patients must be registered both locally and centrally with BTTC.

BTTC patients will be registered with the BTTC Coordinating Center. All eligibility requirements will be checked prior to registration. The status of all regulatory documents will be checked prior to registration. No patient will be entered on protocol if they do not satisfy all regulatory document and eligibility requirements.

2.3.1 Informed Consent

Prior to protocol enrollment and initiation of treatment, subjects must sign and date an Institutional Review Board (IRB) approved consent form.

Registrations must be completed after the patient has signed the informed consent and has been determined to be eligible by the local investigator.

At the time of registration, the following information will be requested by the BTTC Coordinating Center:

- A copy of a completed and signed, protocol specific, Eligibility Checklist form
- One copy of the signed and dated Informed Consent.
- Copies of all source documents to support protocol specific eligibility. Please refer to the Operations Manual for specific source documents required.

2.3.2 Registration at the NCI

Authorized staff must register an eligible candidate with NCI Central Registration Office (CRO) within 24 hours of signing consent for patients enrolling at the lead institution. A registration Eligibility Checklist from the web site (<http://home.ccr.cancer.gov/intra/eligibility/welcome.htm>) must be completed and hand delivered to the BTTC Coordinating Center or sent via encrypted email to the BTTC Coordinating Center Research Nurse. After confirmation of consent, available slot, and eligibility, the BTTC CC research nurse will send the registration Eligibility Checklist to CRO [contact] via encrypted email. CRO staff will call pharmacy to advise them of the acceptance of the patient on the protocol prior to the release of any investigational agents. Verification of Registration will be forwarded electronically via e-mail to the research team with a copy to the BTTC Coordinating Center. A recorder is available during non-working hours.

2.3.3 Participating Site Registration (Not Applicable as of Amendment C)

All patients must be registered through the NCI Central Registration Office (CRO). A protocol registration form and cover memo will be supplied by the Coordinating Center, NCI CCR and updates will be provided as needed. Subject eligibility and demographic information is required for registration. To initially register a subject, after the participant has signed consent, complete the top portion of the form and send to NCI BTTC Coordinating Center's Research Nurse, [name], [contact], email [contact]. Once eligibility is confirmed, send the completed eligibility checklist with the attached supporting source documents to NCI BTTC Coordinating Center's Research Nurse, [name]. If patient is not eligible, please notify NCI BTTC Coordinating Center's Research Nurse, [name]. The CRO will notify you either by e-mail or fax that the protocol registration form has been received. Questions about eligibility should be directed to the NCI BTTC Coordinating Center's Research Nurse, [name].

2.3.3.1 Patient Number for Participating Institutions (Not Applicable as of Amendment C)

Once eligibility has been confirmed by the Coordinating Center, the patient from the participating institution will be registered through the Central Registration Office. A Verification of Registration will be received from the Central Registration Office with the assigned patient ID number. The

patient ID number is unique to the patient and must be written on all data and correspondence for the patient and used to enter data into the C3D database. The participating site will receive the Verification of Registration via fax or email within one working day of registration.

2.3.4 Initiation of Therapy

Treatment may not be initiated until the participating institution receives a faxed or emailed copy of the patient's Registration Verification Letter from the Central Registration Office.

All Patients that are eligible to receive therapy must initiate treatment within 96 hours after the registration.

The BTTC Coordinating Center must be notified in writing of any exceptions to this policy.

2.3.5 Eligibility Exceptions

Eligibility Exceptions will not be granted.

2.4 TREATMENT ASSIGNMENT AND DESCRIPTIVE FACTORS

Patients with recurrent malignant glioma will be enrolled into one of the following groups. Accrual goals and endpoints for each group are determined separately as described in the statistical section.

There will be an accrual of approximately 3-6 eligible patients per dose level to the Phase I component of the study. Patients removed at any time for toxicity are evaluable. Phase I patients removed from study treatment within 28 days for reasons other than toxicity may be replaced.

Cohorts

Number	Name	Description
1	Phase 1 (closed)	Patients with Glioblastoma or Anaplastic Glioma
2A	Phase 2 Group A (closed)	Patients with Glioblastoma with NO prior bevacizumab exposure
2B	Phase 2 Group B	Patients with Glioblastoma with PRIOR bevacizumab exposure
2C	Phase 2 Group C (closed)	Patients with Anaplastic Glioma with NO prior exposure to bevacizumab (Grade III Glioma Group)

Arms

Number	Name	Description
1	Phase 1 (closed)	Combination of sorafenib (7 days on, 7 days off) and everolimus daily over a 28-day cycle at escalating doses

2	Phase 2	Combination of sorafenib (7 days on, 7 days off) and everolimus daily over a 28-day cycle: Sorafenib 400 mg BID PO (days 1-7 and days 15-21) Everolimus 5 mg PO daily (days 1-28)
---	---------	---

There will be a total accrual of approximately 82 eligible patients to the Phase II study (34 recurrent GBM with no prior exposure to bevacizumab, 16 recurrent Anaplastic Glioma with no prior exposure to bevacizumab, and 32 glioblastoma with prior exposure to bevacizumab).

Subjects in Cohort 1 were directly assigned to Arm 1.

Subjects in Cohorts 2A, 2B and 2C will be directly assigned into Arm 2.

2.5 BASELINE EVALUATION

After eligibility is confirmed, complete the following baseline study tasks:

- Patients will complete a baseline MD Anderson Symptom Inventory-Brain Tumor Module (MDASI-BT) (Appendix 13.4) within 14 days (+ 3 working days) after enrollment on the clinical trial. The MDASI-BT will be completed only by the patient, unless changes in vision or weakness make this difficult. If this occurs, then the caregiver or research assistant may read the questions to the patient or assist with marking the severity number or score as described by the patient. A patient caregiver may complete the questionnaires as a patient-preference proxy if the patient's deficits preclude self-report.
- The screening scan can be used as the baseline scan if performed within 14 days of registration on a stable dose of steroids. Patients should not be on a steroid dose higher than 16 mg/day. (Refer to 2.1.1.7 and 2.1.1.8)
- Document baseline adverse events
- For all women of childbearing potential, negative serum pregnancy test within 7 days of starting treatment.
- If treatment will start > 14 days after screening evaluations were completed, then repeat the following labs:
 - CBC, differential, platelets
 - Serum creatinine, phosphate
 - lipase, amylase
 - bilirubin, SGOT
 - PT, PTT
 - Fasting serum glucose and fasting lipid panel
 - Urinalysis with microanalysis; UPC ratio must be obtained if urinalysis has >2+ protein.

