1.1.2 Phase II

1.1.2.1 Primary endpoints:

- 6 month progression free survival rate for glioblastoma patients with no prior bevacizumab exposure treated with everolimus and sorafenib at the maximum tolerated dose as determined in the phase I study.
- 3 month progression free survival rate for glioblastoma patients with prior bevacizumab exposure treated with everolimus and sorafenib at the maximum tolerated dose as determined in the phase I study.
- 6 month progression free survival rate for AG patients with no prior bevacizumab exposure treated with everolimus and sorafenib at the maximum tolerated dose as determined in the phase I study.

1.1.2.2 Secondary endpoints:

- Time to progression and overall survival for recurrent malignant glioma patients (Group A, Group B, and Group C) treated with everolimus and sorafenib measured from time of study enrollment.
- Objective response rate for recurrent malignant gliomas (Group A, Group B, and Group C) treated with everolimus and sorafenib
- Patient related outcome measures

To evaluate the occurrence of symptoms and correlate to disease progression and tolerance to treatment using the MD Anderson Symptom Inventory-Brain Tumor Module (MDASI-BT) self-reporting tool. This will include:

- To evaluate longitudinal changes in symptom measures and determine the impact of the therapy on these parameters.
- To measure symptom burden over the course of therapy to evaluate differences between patients individual symptom severity, overall mean symptom severity, and difference in scores on the interference items between responders and non-responders.
- To describe the variability of symptom severity longitudinally over the treatment course and follow-up period.

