2.0 ELIGIBILITY ASSESSMENT AND ENROLLMENT

Unless otherwise specified, in the Inclusion Criteria for Phase I or Phase II, all patients must meet the General Eligibility Criteria described below. Eligibility waivers are not permitted.

Subjects must meet all of the inclusion and none of the exclusion criteria to be registered to the study. Study treatment may not begin until a subject is registered. See section 2.3 for registration procedures.

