3.0 STUDY IMPLEMENTATION

This is a phase 1 /2 study of everolimus and sorafenib in patients with recurrent high-grade gliomas. Patients must initiate study treatment within 96 hours after registration.

All patients will be monitored for hematologic or serologic evidence of myelosuppression, hepatic injury, renal injury, and electrolyte disturbances and for clinical evidence of other toxicity as is described in section 3.5.

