3.4 QUESTIONNAIRES

The MDASI-BT will be utilized for this portion of the study. Full instruments are provided in the Appendix 13.4. In addition, information regarding demographics and treatment history will be collected as part of the larger study and used in this analysis.

The MDASI-BT consists of 23 symptoms rated on an 11-point scale (0 to 10) to indicate the presence and severity of the symptom, with 0 being “not present” and 10 being “as bad as you can imagine.” Each symptom is rated at its worst in the last 24 hours. Symptoms included on the instrument include those commonly associated with cancer therapies, those associated with increased intracranial pressure, and those related to focal deficits. The questionnaire also includes ratings of how much symptoms interfered with different aspects of a patient’s life in the last 24 hours. These interference items include: general activity, mood, work (includes both work outside the home and housework), relations with other people, walking, and enjoyment of life. The interference items are also measured on 0 - 10 scales. The average time to complete these instruments is 5 minutes. The MDASI-BT has been translated into 18 languages ([24](#), [25](#)).

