HCV RNA- PCR results at screening and/or a history of past infection (even if treated or considered cured).

X¹⁰ To be performed within 14 days (+3 working days) after enrollment on the clinical trial.

X¹¹ All patients with positive HBV-DNA or HBsAg should be treated prophylactically with antiviral agent to be given 1 -2 weeks prior to study drugs, and should continue throughout the entire study period, to

last until at least 4 weeks after the last dose of everolimus.

X¹² If urinalysis has > 2+ protein present, then UPC will be obtained

X¹³ To be performed at the end of each cycle

X¹⁴ To be performed weekly during Cycle 1

X¹⁵ Lab work (blood draws/urine) has a window of +/- 3 days of the cycle

X¹⁶ MRI/CT imaging has a window of within 7 days of new cycle

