each time point. The proportion of patients rating their symptoms to be 7 or greater (on a 0-10 scale) will also be reported. We will construct individual patient profiles for each of the selected symptoms to describe the individual patients' patterns of change over time. We will calculate the mean core symptom severity, mean severity of the MDASI-BT and mean symptom interference at the time of clinical evaluation. Estimates of differences in the mean symptom severity and mean symptom interference between responders and non-responders will be estimated in the intent to treat population. All patients with at least one valid questionnaire will be included in the analyses. Questionnaires completed at study registration will be considered baseline. All questionnaire data received after randomization will be used in the primary analyses.

Differences of at least 2 points will be classified as the minimum clinically meaningful change in the symptom severity and symptom interference measures. For example, an increase of 2 points or more would mean a moderate improvement, whereas a decrease of 2 points or more would be interpreted as moderate worsening. For individual symptoms, a rise in a symptom score means deterioration, whereas a reduced score means improvement of the specific symptom.

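### The baseline MDASI-BT may be completed as late as 13 to 19 days after the first dose, against the calendar and Section 7.2, so a late form is either an on-treatment baseline or no valid baseline

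*Combined protocol and SAP*

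**What the plan says.** **When the baseline form is due.** Section 2.5 asks for it "within 14 days (+ 3 working days) after enrollment on the clinical trial". Footnote X10 in Section 3.5 gives the same window: "To be performed within 14 days (+3 working days) after enrollment on the clinical trial". Neither ties the form to the first dose, yet X10 stands in the calendar's pre-treatment column. Section 5.1.1 sets a third limit: the baseline MDASI-BT is to be submitted within 14 days of registration, without the 3 extra working days.

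**When treatment starts.** Section 2.0: "Study treatment may not begin until a subject is registered". Section 2.3.4: "All Patients that are eligible to receive therapy must initiate treatment within 96 hours after the registration". Section 3.0 repeats it: "Patients must initiate study treatment within 96 hours after registration".

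**What the analysis calls baseline.** Section 7.2: "Questionnaires completed at study registration will be considered baseline". The same section accepts a form as valid if it lies within ten days of its scheduled assessment. It does not say whether, for the baseline form, the ten days run from registration or from the Section 2.5 window. It also does not say how a baseline form completed after the first dose is handled.

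**What the data are for.** The secondary objective in Section 1.1.2.2 is "To evaluate longitudinal changes in symptom measures and determine the impact of the therapy on these parameters".

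**The concern.** A baseline should describe the patient before exposure. The form asks about the present, not the past. According to Section 3.4, "Each symptom is rated at its worst in the last 24 hours". A form completed on drug therefore records on-drug symptoms.

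Fatigue, nausea, anorexia and diarrhea are listed in Sections 10.1.12 and 10.2.12.8 as occurring in more than 20% of patients on each drug. Fatigue, nausea, appetite and bowel pattern are MDASI-BT items (Appendix 13.4). In a patient with a late form, any early drug effect, and any early decline from the tumour, becomes part of the baseline and drops out of the change score. If Section 7.2 is applied literally instead, that patient has no baseline. The stake is the symptom objective, which Section 1.2.6.1 justifies by the need to see whether worsening symptoms offset a survival gain.

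**Working it through.** The plan gives no sample size, power or expected change for the MDASI-BT, so there is no figure to reproduce. The check is calendar arithmetic. It assumes that enrolment and registration fall on the same day (day 0) and that there are no public holidays.

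**1. Latest permitted baseline.** Day 14 plus 3 working days, by weekday of enrolment:

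| Enrolled | Latest day |
|---|---|
| Mon, Tue, Sun | 17 |
| Sat | 18 |
| Wed, Thu, Fri | 19 |

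**2. First dose.** Day 0 at the earliest (Section 2.0) and day 4 at the latest (96 hours).

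**3. Time since first dose at the latest baseline** = latest form day − first-dose day.
- Shortest: 17 − 4 = 13 days. Longest: 19 − 0 = 19 days.
- Without the 3 working days: 14 − 4 = 10 to 14 − 0 = 14 days.

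Any form completed after day 4 is on drug if the 96-hour rule is kept.

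**4. Exposure by then.** Everolimus is daily, so 13 to 19 dosing days are complete. Sorafenib is given on days 1–7 and 15–21. After 13 complete days, 7 are sorafenib days; after 19, there are 7 + 5 = 12. Sections 10.1.13 and 10.2.13 put steady state within 7 days for sorafenib and within two weeks for everolimus.

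**5. Distance to the first follow-up form.** It is due with the 4-week scan, nominally 28 days after first dose. The interval shrinks from 28 days to between 28 − 19 = 9 and 28 − 13 = 15 days. Under the ten-day rule a 4-week form is valid from 28 − 10 = 18 days after first dose. With a same-day start, a baseline on day 18 or 19 can coincide with, or follow, the earliest valid follow-up form.

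**6. If the ten-day rule counts from registration.** The latest valid baseline is day 10, which is 10 − 4 = 6 to 10 − 0 = 10 days after first dose. Later forms are invalid, so the baseline is missing. If the rule counts from the Section 2.5 window, it removes none of the 13 to 19 days.

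**7. Effect on the change score.** Let f be the share of the true change already present when the form is completed. Observed change = (1 − f) × true change. For a true change of 2 points, the minimum meaningful change in Section 7.2:

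| f (assumed) | Observed change |
|---|---|
| 0 | 2.0 |
| 0.25 | 1.5 |
| 0.50 | 1.0 |
| 0.75 | 0.5 |
| 1.00 | 0 |

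The documents give no value for f.

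**8. With the form before first dose.** Time on drug at baseline is 0 days and the interval to the 4-week form is the full 28 days.

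**The case against.** The best reply is that the plan already intends a pre-treatment form. The calendar column says so, the other tasks in Section 2.5 prepare for treatment, and Section 7.2 fixes baseline at registration. The 14 days in Section 2.5 may be the Section 5.1.1 submission deadline carried over by mistake. With the ten-day rule, a day-17 form would simply be invalid, giving a missing baseline rather than a biased one.

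Much of this stands as a reading of intent, and it is why the late form cannot be called a biased baseline without qualification. It does not remove the problem. Section 2.5 and X10 are the texts that give sites a due date, and they allow the late form. If Section 7.2 overrides them, compliant patients lose their baseline. Even the favourable reading of the ten-day rule leaves 6 to 10 days on drug. Section 7.2 is also loose on timing elsewhere: it refers to data received after randomisation in a trial that assigns patients directly.

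It is also fair to say that the planned analysis is mainly descriptive, with no formal test of change from baseline. Steady-state concentration does not show that symptoms have reached a plateau. Section 10.1.12.1 places rash and hand-foot reaction generally in the first six weeks, and a form at 13 days falls on the last day of a sorafenib off week. Both points limit the size of the effect, not its existence.

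**Conclusion.** The point holds in limited form. The texts contradict each other, and a compliant baseline can be taken 13 to 19 days after first dose, or 6 to 10 days if the ten-day rule runs from registration. For a late form used as baseline, the change before it is absorbed. The loss runs from none to all of a 2-point change, depending on an assumed fraction. How many patients have late forms cannot be known from the documents.

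A reader might infer that the effect of therapy on symptoms is lost altogether, or that a 2-point worsening will be recorded as 0. The documents do not support either. Patients with a pre-dose form are unaffected, later change is still measured, and 0 is only the extreme of the range.

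A reader might also infer that the late baseline is what prevents the trial from weighing symptoms against survival. It is not: with no control arm, even a clean baseline shows change on therapy, not change caused by it, and there is no concurrent comparison to establish a survival gain. The primary progression-free survival endpoints and the sample size are untouched. This should be corrected, but it bears on one secondary objective.

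**What to change.** - **Section 2.5 and footnote X10:** require the baseline MDASI-BT after consent and before the first dose of either drug.
- **Section 5.1.1:** align the baseline questionnaire timeframe, keeping the date of completion distinct from the date of submission.
- **Section 7.2:** define baseline as the last valid form before first dose. State the reference date for the ten-day rule as it applies to that form.
- **Forms already collected after first dose:** treat them as on-treatment data and report their number and timing. Show change from baseline with and without the patients concerned as a sensitivity analysis.

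The cost is a wording change and a form that Section 3.4 says takes 5 minutes, which fits a visit already taking place. Some patients already enrolled will have no usable baseline. The prospective gain is limited to remaining Group B patients, since Section 2.4 marks phase I and Groups A and C as closed.
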